Real world applicability of a study is enhanced if exclusion criteria are kept to a minimum. However, clear confounds should be avoided. Miller, et al., found that in young surgical patients, diabetes, cancer, kidney disease, hypertension, and abnormal BMI all significantly increased the chances of wound complications, while COPD, smoking, age, and HIV status did not.⁸² Yang, et al., found that smoking, hypertension, age, diabetes, and obesity did not delay VLU healing, and that males were more likely to have delayed VLU healing.⁸³ In contrast, Lane, et al., found that smoking dramatically reduced pressure injury healing, and McDaniel and Browning found that smoking negatively impacts chronic wound healing by impairing neutrophil function and fibroblast activity; decreasing both white and red blood cell production; increasing carbon monoxide, hydrogen cyanide, and other toxic compounds; causing tissue hypoxia; and causing the release of catecholamines.^{84,85} Smoking cessation programs led to improved wound healing.^{84,85} Parker, et al., found that delayed venous ulcer healing was correlated with living alone, ulcer duration > 24 weeks, and age > 70 years.⁸⁶ A review of studies of venous leg ulcer management demonstrated that 12 weeks were sufficient to determine if a treatment was effective or not.⁸⁷

2. Research Questions/Aim:

This study's primary purpose is to determine if an *improvised dressing*, made from inexpensive materials available for purchase in rural as well as urban settings, is a safe and effective, culturally and medically acceptable choice for managing sickle cell leg ulcers in a tropical climate. Three research questions will be addressed:

(1) Is the *improvised dressing*, consisting of a cut-to-fit new plastic bag sealed at the periwound with zinc oxide paste, safe and effective (see definitions, below) when compared with usual practice (saline-soaked gauze) and when compared with an advanced wound dressing (PMD), on sickle cell leg ulcers (SCLUs) in Jamaica?

(2) Does use of the *improvised dressing*, when compared with usual practice, improve the quality of life of patients (decrease pain, increase ability to engage in desirable activities, decrease wound-related materials costs, decrease time required to perform dressing changes, improve Wound QoL scores, and improve ASCQ-Me pencil-and-paper interview scores) with SCLUs in Jamaica?

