(3) Is the *improvised dressing* culturally acceptable to health care providers, patients, and families for managing SCLUs in Jamaica?

The expected study outcome is improvised dressing superior effectiveness and quality of life, when compared with usual practice, without increased safety and acceptability issues.^{13,59,60,62} The improvised dressing is likely to be the least expensive choice, with the added benefit of being available as first aid treatment throughout Jamaica. The advanced dressing is likely to be more expensive with respect to materials costs, although fewer dressing changes are anticipated and pain medication expenses are likely to be reduced. Based upon the review of the literature, no serious infections or other safety issues are anticipated for any group. However, to ensure that complications are not overlooked, in addition to the onsite researchers' vigilance, weekly wound photos will be assessed for complications (signs of infection, wound deterioration, or clinically relevant maceration) by two off-site blinded wound experts, Drs. [name] and [name].

Definitions:

Sickle cell leg ulcer – a wound in a HbSS or HbS β^0 positive patient, open greater than one month,⁷ below the level of the knee excluding the plantar surface of the foot.

Closed wound -100% epithelialized with no discernible scab or exudate production (paper napkin remains dry when lightly pressed against area, and no recurrence in the subsequent two weeks)

Safe – infection and other complications (healing-impairing maceration, keloid, and contracture rates) not statistically significantly higher than usual practice, with no major adverse events attributable to the method

Effective – ulcer closure rates or ulcer surface area reduction rates not statistically significantly lower than usual practice

Acceptable – average acceptability scores of 4 or higher on a 1-5 scale

3. Methods and Materials

a. Study design

This study will be a targeted-blinded (the off-site wound experts and the local physicians verifying wound closure and/or complications will be blinded to the randomization group), randomized controlled trial with three arms: (1) usual practice (negative control), (2) the improvised dressing, and (3) the advanced dressing (positive control). The expected outcome is improvised and advanced dressing superiority.

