Study patients will be randomized into groups 1, 2, or 3 immediately AFTER initial thorough wound cleansing/debriding by the nurse or physician. Randomization will be accomplished using an electronic random number generator (an app).

After a member of the UHWI surgical team performs the initial cleansing/debriding, the control group (1) will have their ulcer dressed as usually done at UHWI. Wounds are dressed with saline-soaked gauze, covered with dry gauze. One wrap of stretch gauze will hold the dressing in place. Patients will clean the wound by vigorously wiping with gauze soaked in homemade normal saline (1 tsp salt/500ml water bottle), center to edges, at each dressing change, unless already very clean. Clean wounds will simply be irrigated with normal saline at each dressing change. Patients experienced with using papaya for debridement of their ulcers may apply it only to the open wound, avoiding contact with the periwound, to remove slough or eschar. If patients observe green exudate, they are permitted to add one teaspoon of vinegar to their bottle of saline. Dressings in group (1) will be changed daily. The dressings will be soaked off if they become adherent.

After initial cleansing/debriding, patients in the improvised dressing group (2) will then have a thin layer zinc oxide paste applied to the dried periwound, carefully avoiding the open wound.⁹⁷ A piece of a clean new plastic bag (food-grade World Star 1 mil LD bags, or the equivalent, purchased from the Papine Market across John Golding Road from the University of the West Indies), cut slightly larger than the ulcer will be gently conformed to the moist wound contours and sealed onto the zinc oxide paste. The bag will be fenestrated with a small slit using a number 11 scalpel or clean scissors prior to placing it on the ulcer in order to allow excess fluid to escape. The edges of the slit will be approximated. Clean gauze will be placed lightly over the slit to capture escaping fluid. One wrap of stretch gauze will hold the dressing in place. Patients will be instructed to change the dressings daily, irrigating with normal saline at each dressing change.⁶

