After initial cleansing/debriding, the advanced dressing group (3) will have a cut piece of a 4"x24" standard (pink) PMD roll large enough to extend at least 0.5 cm beyond all open and closed (inflamed or damaged) wound edges applied as per the Instructions for Use (the periwound is blotted dry, but the wound bed remains moist from the final saline rinse). One wrap of stretch gauze will hold the PMD dressing in place. The approximate open wound edges will be marked on the dressing backing. As per the manufacturer's instructions for use, patients will change the dressings when saturation reaches any of the wound edges, as indicated by a change in color on the backing of the dressing, visible through the stretch gauze. Routine rinsing will not be performed; the wounds will be rinsed at dressing changes only if visible loose debris is present.

All study patients will receive education about their illness and pain medication prescriptions per usual protocol. Patients are advised to use a compression wrap whenever their foot is dependent, as often as they are able to tolerate it. They will each be given a zipper-bag to contain and keep their wound management supplies clean.

Patients will be required to come to the UHWI surgical clinic dressing area in person weekly during the initial 4 weeks of study enrollment so that wound photos can be taken and the data for the ten dependent variables that are to be assessed weekly can be obtained. If their SCLU is clean without evidence of complications, patients/families who demonstrate the ability to take adequate pictures of their study SCLU with their mobile devices may instead send photos of their wound and their data collection sheets to the research team via end-to-end encrypted text messaging system (WhatsApp). All patients must agree to come to UHWI at least once per month to avoid being withdrawn from the study. Appointment times will include evenings and Saturdays to accommodate the schedules of students and employed patients.

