Weekly, de-identified photographs will be sent by the Principal Investigator to be viewed by two blinded wound experts ([name] and [name]) off site. If the blinded experts, or anyone else involved in the study, expresses concern that a patient is exhibiting signs of possible infection, maceration that is delaying healing, or wound deterioration, a physician at UHWI or the SCU who is not otherwise involved in the study will be asked to evaluate that patient. The patient's dressings will be removed prior to this evaluation so that their treatment group will not be revealed to the physician (the evaluation by the physician is thus blinded to treatment group). If the physician determines that the patient's condition has not improved with the prescribed treatments (e.g., antibiotics), the patient will be withdrawn from the study. Any

patient who transitions out of the group to which they were randomized for any reason will receive usual treatment for their ulcer for the remainder of their 12 week study period.

When the treatment personnel at UHWI or the blinded remote observers state that the patient's wound appears to be closed, a physician at UHWI or the SCU who is not otherwise involved in the study will be asked to evaluate that patient. The patient's dressings will be removed prior to this evaluation so that their treatment group will not be revealed to the physician. Wound closure is defined as 100% epithelialized with no discernible scab or exudate production (a paper napkin blotting the area remains dry). Patients will be reassessed two weeks later to verify that the wound was truly closed and did not immediately recur.

Patients who are diagnosed with wound closure or have completed the 12 week study period will be taken aside privately and asked to rate the acceptability of their treatment using a 5 point Likert Scale. A family decision-maker will also be privately asked to rate the acceptability of the treatment. One of the research team members will enter this basic acceptability data for the patient and the family on the patient's Data Collection Tool. At that point, the patient will graduate from the study. However, patients and families will be instructed to return to UHWI for follow-up if a complication or recurrence develops. Any delayed complications (e.g., recurrence within 3 months) will be recorded on the patient's Data Collection Tool by the nurse or physician to whom the patient reports it.

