SCLUs are often disabling, scarring, and exquisitely painful. The research literature suggests that both the improvised dressing and the advanced dressing can decrease pain. The advanced dressing has also been shown to decrease scarring. However, children ages 13 - 18 are an especially vulnerable population. They are included in the study because this is the peak age group for SCLU formation, and therefore they are the most likely to benefit if the results can be generalized to them.¹⁵

5. Limitations

Blinding is a challenge inherent to studies of wounds. Although the the healthcare professionals who will monitor and verify wound closure and complications (outcomes) will be blinded, it is not possible to blind the participants or the research team members, because they will provide the wound management in this study.

Despite the incentives to remain in the study (phone cards monthly and wound management supplies at the conclusion of the study), it is possible that there will be a substantial dropout rate, because it is easy for patients with SCLUs to become discouraged, and they may feel that they have derived the major benefits of joining the study after the first few weeks.

All of the published studies of improvised dressings describe wound care performed by health professionals based in urban hospitals or long term care facilities. Although this study will be conducted in a tropical outpatient setting, it too is being conducted by health care professionals in an urban area. Also, Jamaica is significantly more developed than many of the countries for whom the improvised dressing educational program may be beneficial. Therefore, this study may not uniformly generalize to rural areas of tropical developing countries, where health professionals are absent.

6. Acknowledgments:

The researchers would like to thank all participants in the study.

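### Blinding of the complication assessment, and to a lesser extent of closure, is not ensured for the improvised-dressing arm: only that arm has zinc oxide paste around the wound, and no step removes or masks it

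*Combined protocol and SAP*

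**What the plan says.** Section 3a (Study design) describes a trial in which treatment is open but certain assessors are masked. It names the off-site wound experts and says that "the local physicians verifying wound closure and/or complications will be blinded to the randomization group". Section 5 (Limitations) repeats the claim: "healthcare professionals who will monitor and verify wound closure and complications (outcomes) will be blinded".

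Section 3h (Data collection) gives the means. When anyone raises a possible complication, or when a wound appears closed, a physician with no other role in the trial examines the patient, and the "dressings will be removed prior to this evaluation so that their treatment group will not be revealed to the physician". For complications the text concludes from this step that the evaluation is blinded. The off-site experts receive weekly de-identified photographs.

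The same section sets out the three dressings:

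- **Group 1 (usual practice):** "Wounds are dressed with saline-soaked gauze, covered with dry gauze".
- **Group 2 (improvised dressing):** patients "will then have a thin layer zinc oxide paste applied to the dried periwound, carefully avoiding the open wound", and the plastic is then sealed onto the paste. At daily changes the stated cleansing is irrigation with saline.
- **Group 3 (advanced dressing):** "the periwound is blotted dry, but the wound bed remains moist from the final saline rinse". There is no routine rinse at dressing changes.

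Section 2 (Research Questions/Aim) describes the improvised dressing as "consisting of a cut-to-fit new plastic bag sealed at the periwound with zinc oxide paste".

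**The concern.** Taking a dressing off conceals the group only if the exposed skin looks the same in every arm. Paste is described in one arm alone, and that arm is the one under test. If some of it remains, a physician or photo expert who knows the three procedures could recognise group 2.

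Participants and treating staff know the allocation, so these assessors are the plan's main protection against biased outcome judgement. Their findings feed the definitions of safe and effective in section 2. Views that could tilt a judgement are on record in both directions: section 1b raises the worry that plastic may promote infection in the tropics, and section 3a expects the improvised dressing to do better than usual practice. Healing-impairing maceration is a counted complication, and it is judged on the same skin that carries the paste.

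There is also a knock-on effect. Under section 3h, a physician's finding that a patient has not improved with prescribed treatment leads to withdrawal. Under sections 3a and 3i, such patients leave the non-inferiority analysis. An unmasked judgement could therefore affect who is analysed as well as what is recorded.

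**Working it through.** The plan gives no figure to reproduce here, so the check sets the dressing procedures beside the masking steps.

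**Step 1. Is there an arm-specific mark?** Group 1 has gauze only and group 3 has a polymeric membrane dressing on dried skin. No paste is described for either. Group 2 has a "thin layer zinc oxide paste applied to the dried periwound, carefully avoiding the open wound". The mark is specific to group 2 and lies on the surrounding skin.

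**Step 2. Does any step remove it before the physician looks?** The stated step is dressing removal. Group 2's irrigation with saline belongs to the dressing change, and the text does not say that it clears the paste or that it comes before the physician's examination. No instruction to wipe the surrounding skin appears in section 3h or elsewhere.

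**Step 3. Does any step remove or hide it before the photographs?** The stated measure is de-identification. Nothing covers skin preparation, cropping, or when in the dressing change the picture is taken. After the first 4 weeks, patients or families may take the pictures themselves if the ulcer is clean and free of complications.

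**Step 4. Does the blinding conclusion follow?** It needs a further premise, that the skin looks alike in all arms once the dressing is off. The plan neither states this nor provides for it. The conclusion is therefore not secured.

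**Step 5. Which outcomes are exposed?**

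| Outcome | How it is judged | Exposure |
|---|---|---|
| Complications (infection, healing-impairing maceration, deterioration) | Clinical judgement by the physician; photo review | Main exposure |
| Closure | Full epithelial cover, no scab, dry blot test, recheck at two weeks | Smaller |
| Surface area | Software measurement from a photograph | Outside this point |

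**Step 6. How large is it?** Sections 3c and 3f plan about 30 patients per group, so 30 / 90 = one third of patients are in the affected arm. With one photograph a week for up to 12 weeks, that is at most about 30 × 12 = 360 photo reviews in that arm, plus any physician checks. This counts opportunities for recognition and does not measure bias. A bias estimate would need the frequency of visible residue, the assessors' ability to read it, and complication rates by arm. The documents give none of these.

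**The case against.** The strongest reply is that visible residue is an inference. Section 2 counts the paste seal as part of the improvised dressing, so removing the dressing could mean removing the paste. Saline irrigation may take off some of it, and new paste goes onto dried skin, so a photograph taken between the two might show little. The evaluating physician has no other role in the trial and may not know what paste signifies. All of this stands. It rules out saying that blinding fails, but it does not supply the missing instruction. If the sponsor intends the paste to come off, the protocol should say so.

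A second reply is that the photo experts are an added safety net, and that anyone in the study, including unblinded staff, can trigger a referral. Detection of complications is then partly open whatever is done about paste. That also stands, and it limits what the fix can achieve. The physician's confirmation, however, is the step claimed to be blinded.

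A reader might go further and infer that assessors can identify the test arm on sight, that paste hides warmth or maceration, or that closure is compromised as much as complications. The documents do not support these readings. They do not say that paste remains visible. Periwound warmth appears only as a sign of infection in the exclusion criteria, before any paste is applied. The cited plastic-wrap studies describe maceration as quickly resolved or clinically unimportant. Nor do the documents say whether paste is still used at the two-week closure recheck, or that the blinded assessors share the authors' expectations.

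**Conclusion.** The plan claims blinded assessment of complications and closure but does not secure it for the improvised-dressing arm. The gap matters most for complications, which rest on clinical judgement. It matters less for closure, and this point does not reach software-measured surface area. It touches one of three arms. The direction and size of any resulting bias are unknown and cannot be derived from the documents.

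The conclusion rests on two assumptions: that some paste can remain on the skin after the plastic comes off, and that an assessor could recognise it. Both are reasonable, and neither is documented. This is a gap that should be closed because doing so is cheap. It is not a demonstration that the assessments will be biased.

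**What to change.** Add the following to the visit, photograph and evaluation instructions in section 3h:

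1. Before each study photograph and each blinded physician evaluation, unblinded staff (or the patient, for home photographs) wipe the surrounding skin only, in the same way in all three arms, until no dressing residue is visible.
2. Each arm's own wound-bed cleansing or rinsing stays as written. Adding wound cleaning in every arm would conflict with group 3's instruction against routine rinsing and would alter the treatment being compared.
3. Photographs are taken before new paste is applied.
4. Patients are asked not to name their dressing to the evaluating physician.

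Optionally, the physician and photo experts record a guess of the group, so that the success of blinding can be reported. Where residue cannot be removed, section 5 should list possible unblinding as a limitation.

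The cost is a few sentences of text and a minute or two per photograph or evaluation, plus one form item if guesses are recorded. Home photographs will depend on patients following the step. Randomisation, outcomes and sample size do not change.

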Decrease in SCLU surface area will be used to answer research question 1. Conducting a power analysis for this study is challenging because only one study of SCLUs has demonstrated a statistically significant outcome, and the effect size was obscured by high standard deviations, which is a common problem in studies of wounds.⁸ Improvised plastic dressings similar to the study dressings were used in 49 chronic pressure ulcers in elderly patients, which are often slow to close, if they heal at all.⁶⁰ These two studies demonstrated a significant difference with confidence intervals of 99% with ~25 patients per group. Based upon these sample sizes and the Central Limit Theorem, it is reasonable to set the minimum sample size for this study at 30 patients per group,.^{88,89}

d. Variables

Dependent Variables (measured weekly - tools and permissions in appendices):

- 1. Persistent wound pain (using the Faces Pain Scale Revised (FPS-R))
- 2. Procedural (dressing change) wound pain
- 3. Amount of pain medication taken, including a total number of morphine equivalents plus non-opioid pain medications
- 4. Approximate time spent standing, or sitting with leg dependent without compression (estimated hours per week)
- 5. Patient overall quality of life (assessed with the ASCQ-Me Emotional, Pain, Social Functioning, Stiffness, and Sleep Impact Short Forms)
- 6. Patient wound-specific quality of life (assessed with the Wound QoL tool)
- 7. Materials costs (estimated, using lowest retail costs on Amazon.com for items not on the UWI price sheets)
- 8. Time spent performing dressing changes
- 9. Wound complication rates (e.g., wound infection, healing impairing maceration, wound deterioration)
- 10. Change in wound surface area (measured in cm² electronically using software that automatically corrects for skew, such as HealthEPix or WoundMatrix)⁹⁰

Dependent Variables (measured one time, at graduation from study)

- 11. Wound closure time, in weeks (see definitions; verified two weeks later. Omit patients whose wounds did not fully close they are included in 10., above.)
- 12. Acceptability of dressing choice patient (5 point Likert scale and qualitative free response)
- 13. Acceptability of dressing choice family member (5 point Likert scale and qualitative free response)
- 14. Acceptability of dressing choice UHWI staff (5 point Likert scale and qualitative free response)

Independent Variables (documented at initial study visit):

1. Patient gender

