- Based upon previous studies and the Central Limit Theorem, an estimated 90 participants (~30 per group) may be required for the differences between groups to reach statistical significance.^{12,23,88,89,96} Up to 120 patients will be recruited to allow for a 25% dropout rate. Based upon the literature review, pain, costs, wound size, and quality of life are expected to be significantly improved using the improvised dressings. However, because SCLUs are, historically, very slow to heal and often enlarge, complete wound closure is not an expected outcome for all patients.

g. Procedures for recruitment and consent

The study will be advertised using free community information channels such as church bulletins and radio outlets. Social media sites such as the CAIHR Facebook page will also be employed. Qualifying patients in the SCU database from up to two years prior to the study initiation will be called by the UHWI surgical team, alerting them to the dates for registering to participate. Flyers will be posted at the SCU in advance. Consent will be obtained by a member of the research team while the potential participant is waiting to be seen for wound care.

h. Data collection

The site for this study is the surgical clinic dressing area at the University Hospital of the West Indies (UHWI), Mona, Jamaica. The adjacent Sickle Cell Unit (SCU) will refer any SCLU patients to UHWI during the study period. UHWI is consistently well staffed with competent Jamaican health professionals. The UHWI surgical team will lead the study. Relatively few Jamaicans live or work in air-conditioned environments, ^[data in appendices] allowing the results from this out-patient population to translate to less developed tropical countries.

To ensure consistency, members of the research team will practice until they can demonstrate competency with all three dressing change procedures and with explaining the study forms prior to study patient recruitment.

Enrollment in the study will begin within two weeks of the day the Principal Investigator arrives at the Mona campus and will close 60 days later, or when a maximum of 120 patients have enrolled. All sickle cell positive patients presenting to UHWI with lower leg ulcers during the enrollment period will be screened for eligibility to enter the study. Each patient's data will be recorded for a total of 12 weeks, or until their SCLU has been closed for 2 weeks, whichever comes first.

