Patients (and adult relatives of eligible patients under the age of 18) will have the study explained to them by one of the members of the UHWI surgical team. Questions will be addressed thoroughly. Families will be assured that if they choose not to participate in the study, the SCLU will be managed with usual practice. The patient (and a decision-maker of the family, in the case of a minor) must sign the consent for the patient to be enrolled in the study.

Immediately after consent is obtained, the study tools (Patient Data Collection sheet, Faces Pain Scale – Revised (FPS-R), ASCQ-Me, and Wound QoL) will be explained to the patient and family. Baseline persistent pain will be assessed using the Faces Pain Scale – Revised (FPS-R).

All of the initial independent variable data will be handwritten onto the patient's individual Study Data Collection Form upon enrollment in the study. The largest SCLU upon initial presentation is the study wound. All SCLUs will be measured for the first four weekly visits to UHWI. If two or more SCLUs in close proximity join during the first four weeks, the sum of the initial areas will be the initial wound size.

The SCLU(s) will be measured initially by placing two pieces of clear plastic on top of one another and tracing the wound edges. The plastic that came in contact with the wound(s) will be discarded and the plastic with the markings on it will be added to the patient's documentation so that the patient can be shown if the SCLU is becoming smaller at subsequent dressing changes. SCLU area will be measured in cm² electronically from a photo, using software such as HealthEPix or WoundMatrix.

Patients (with the support of their families) will be taught to evaluate and document persistent and dressing change pain, pain medication doses taken, time spent and supplies used at dressing changes, their activity, and their use of compression on a checklist-style Study Continuation Form daily. They will either provide the research team with their weekly summary and wound photo via WhatsApp, or they will attend the clinic weekly so that the research team can obtain this data. Two encrypted USB drives containing the data, including wound photographs, will be updated weekly on an alternating schedule and stored in a securely locked file in the UHWI surgical clinic dressing area, along with the paper study documentation.

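### Patient and family acceptability is rated only at closure or week 12, so the mean compared with 4 may leave out those who stopped attending or were withdrawn

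*Combined protocol and SAP*

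**What the plan says.** Section 3d lists acceptability to the patient, the family member and the staff as variables 12 to 14, under the heading "Dependent Variables (measured one time, at graduation from study". Section 3h then says who is asked: "Patients who are diagnosed with wound closure or have completed the 12 week study period will be taken aside privately and asked to rate". What they score, on a five-point scale, is how acceptable they found the treatment they received. A family decision-maker is asked too, and the patient graduates at that point. The criterion under Definitions in section 2 is "average acceptability scores of 4 or higher on a 1-5 scale".

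Section 3h also describes ways of leaving early:

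- Non-attendance: "All patients must agree to come to UHWI at least once per month to avoid being withdrawn from the study".
- Withdrawal after a blinded physician finds no improvement.
- Change of group: any "patient who transitions out of the group to which they were randomized for any reason" receives usual treatment for what is left of their 12 weeks.

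None of these carries an instruction to collect a rating. On duration, the same section says each patient's "data will be recorded for a total of 12 weeks, or until their SCLU has been closed for 2 weeks", whichever is earlier. Section 3f plans for losses: "Up to 120 patients will be recruited to allow for a 25% dropout rate".

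Section 3i compares the groups on all 14 dependent variables by intent-to-treat. It treats question 3 with descriptive statistics on Likert items about use of the improvised dressing. It does not say how missing ratings, or ratings made after a switch, are handled.

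**The concern.** Whether the improvised dressing is acceptable is part of the study's stated purpose and the whole of research question 3. The answer for patients and families is a mean held against a fixed mark. If ratings come only from those who reach closure or week 12, that mean describes people who stayed. Those who gave up on a dressing, and their families, hold views that question 3 needs. Section 1b records that several earlier moist dressings at the Sickle Cell Unit gave no superior results, were not accepted by patients, or both, so non-acceptance is a real possibility here. Intent-to-treat is named, but it cannot supply ratings that nobody collected.

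A second, smaller issue concerns patients in groups 2 and 3 who move to usual treatment and stay to week 12. They may be asked to rate their treatment when the dressing in use is no longer the randomised one. If the answer refers to usual practice but is counted in the randomised arm, that arm's mean is partly a rating of something else. This cannot arise in group 1, which receives usual practice throughout.

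**Working it through.** **The plan's own figure.** Section 3f gives 90 participants and a 25% dropout rate: 90 / (1 − 0.25) = 120, which matches the stated maximum. Per arm, 120 / 3 = 40 randomised, of whom 40 × 0.75 = 30 complete and 10 do not. The 25% covers dropout from all causes. It is used here as an upper case for the unrated share, because some patients counted as dropouts may still be rated at week 12.

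**Assumptions.** The documents give no acceptability scores. The rated mean m, the mean d that the unrated would have given (anywhere from 1 to 5), the unrated shares of 10% and 5%, and the number of switched patients are all assumed. Only p = 0.25 comes from the plan.

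**Selection.** All-randomised mean = (1 − p) × m + p × d.

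| m | p | d = 1 | d = 5 |
|---|---|---|---|
| 4.0 | 0.25 | 3.00 + 0.25 = 3.25 | 3.00 + 1.25 = 4.25 |
| 4.0 | 0.10 | 3.60 + 0.10 = 3.70 | 3.60 + 0.50 = 4.10 |
| 4.2 | 0.25 | 3.15 + 0.25 = 3.40 | 3.15 + 1.25 = 4.40 |
| 4.2 | 0.05 | 3.99 + 0.05 = 4.04 | 3.99 + 0.25 = 4.24 |
| 4.5 | 0.25 | 3.375 + 0.25 = 3.625 | 3.375 + 1.25 = 4.625 |
| 4.5 | 0.10 | 4.05 + 0.10 = 4.15 | 4.05 + 0.50 = 4.55 |

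**Break-even.** The all-randomised mean equals 4 when d = (4 − (1 − p) × m) / p.

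- m = 4.25, p = 0.25: (4 − 3.1875) / 0.25 = 3.25. The pass reverses only if the unrated would average below 3.25.
- m = 4.5, p = 0.25: (4 − 3.375) / 0.25 = 2.5. It reverses only below 2.5.
- m = 4.5, p = 0.10: (4 − 4.05) / 0.10 = −0.5, which is off the scale, so the pass cannot reverse.
- m = 3.8, p = 0.25: (4 − 2.85) / 0.25 = 4.6. A fail becomes a pass only if the unrated would average 4.6 or more.

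**Switched patients.** Suppose k of n raters in group 2 or 3 score usual practice instead of the randomised dressing, and the two scores differ by g points. The arm mean then moves by k × g / n, in the direction of g. With n = 30 and g = 1, k = 3 gives 3 / 30 = 0.10 and k = 6 gives 6 / 30 = 0.20.

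**The case against.** The strongest reply is that the plan reaches more people than the rating rule suggests. Patients who leave their group go on with usual treatment to the end of their 12 weeks, and those who complete 12 weeks are rated. On that reading, switched patients who stay are covered. Only those who stop attending, or are withdrawn and not followed, go unrated, and they are the hardest to reach by any method. This narrows the selection issue but does not remove it. Section 3h does not say whether a withdrawn patient is still followed to week 12, and section 5 accepts that dropout may be substantial.

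On switched patients, a reader might infer that ratings of usual practice will be credited to the study dressings. The documents do not support this. Section 3d names the variable as acceptability of the dressing choice, and section 3i ties the Likert items to use of the improvised dressing. Both suggest that the study dressing is meant, though neither settles what a switched patient is rating. Counting a week-12 rating in the randomised arm is also consistent with intent-to-treat, and a rating taken at the switch answers a somewhat different question. The objection therefore reduces this part to an ambiguity in wording.

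It is also fair that question 3 is descriptive, that rating at the end of treatment is a legitimate choice, and that section 3i already plans frequencies. But frequencies among the rated do not commit the report to giving the number randomised beside them.

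**Conclusion.** The point holds as a gap in collection. As the text stands, the patient and family means may rest on a selected set, and later analysis cannot recover ratings that were never taken. The gap decides the verdict only when the rated mean is near 4; well above 4, or with few unrated, the verdict is safe. These sizes rest on assumed scores and on 25% as an upper case for the unrated share.

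A reader might infer that the omission flatters the improvised dressing. That is plausible but not shown: section 5 gives reasons for leaving in both directions, namely discouragement and having already gained the main benefit. Nor can it be said that no exit rating exists, because the appendix forms were not available.

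It would also go too far to call staff ratings unaffected. Section 3d places them under the same graduation heading, while section 3i describes a survey of all participating providers; which applies is unclear. The wound outcomes are outside this point. It merits a change because the change is cheap and must be made before patients leave.

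**What to change.** 1. At withdrawal or switch, or at the last clinic, phone or WhatsApp contact, ask the patient and the family decision-maker the existing Likert item, worded about the dressing to which the patient was randomised. Ask only those willing to be contacted. A channel exists already: "They will either provide the research team with their weekly summary and wound photo via WhatsApp", or attend weekly.
2. Word the graduation item in the same way, so that a switched patient knows which dressing is being rated.
3. Report the patient and family means with and without the exit ratings, and say in advance which is compared with 4.
4. Report by arm the number rated out of the number randomised, with reasons for leaving.
5. For ratings still missing, give low and high bounds as sensitivity results only, not as the decision rule.
6. State whether staff ratings are tied to each patient's graduation or come from the provider survey.

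The cost is one existing item asked at one more time, a few extra contacts and a few lines of analysis text. The sample size and treatment do not change. The downsides are that some leavers will stay unreached, that ratings will come at differing times, and that the reported mean may be lower.
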